**Updated version, 6.0**

**27 June, 2022**

## **1. Background and rationale:**

[figure not shown]
Pregnant and breastfeeding women in South Africa are at very high risk of HIV acquisition and vertical HIV transmission during pregnancy, labour and breastfeeding [1-4]. One-third to half of perinatal HIV transmission occurs in women who are seroconvert during the pregnancy and post-partum period [5-6]. Effective use of pre-exposure prophylaxis (PrEP) could contribute to eliminating maternal HIV acquisition, and hence mother to child transmission (MTCT) of HIV. However, PrEP efficacy requires high levels of adherence, and adherence requires high levels of acceptability, yet there are few data on acceptability and adherence in pregnant and breastfeeding women in high HIV prevalence communities.

**Risk of HIV acquisition in pregnant and breastfeeding women:** Despite increased access to HIV testing and counseling, condom promotions and antiretroviral therapy for male partners, maternal HIV incidence continues to be very high during and after pregnancy. In South Africa it is estimated that maternal HIV incidence was as high as 10.7 per 100-person years (PY) which is highest in urban health facilities at 12.4 per 100 PY [3]. High HIV incidence in pregnancy contributes to the majority of infant HIV infection [1, 4]. Mothers who seroconvert after their first antenatal visit account for approximately 34% of vertical transmission [3]. In a recent meta-analysis, vertical HIV transmission risk was significantly higher in women with incident versus chronic HIV infection in the postpartum period (odds ratio of MTCT in pregnancy [OR]=2.9, 95% confidence interval [CI]=2.2, 3.9) or in pregnancy and postpartum periods combined (OR=2.3, 95% CI=1.2, 4.4) [4]. Biological mechanisms of increased susceptibility of HIV acquisition during pregnancy and breastfeeding may be due to hormonal changes that alter genital mucosal surfaces or distribution of target cells at these surfaces [3]. However, behavioral factors also play a role including increased condomless sex during pregnancy, (multiple) sex partners of unknown serostatus and substance use during pregnancy and breastfeeding periods [3].

**Interventions to prevent maternal HIV acquisition:** We urgently need effective interventions to reduce HIV incidence in pregnant and breastfeeding women. PrEP is one of the only female-controlled methods that is effective for preventing HIV acquisition and safe in pregnancy. Recent meta-analyses demonstrated that use of tenofovir is not associated with increased adverse events during pregnancy or breastfeeding [6-11]. In new guidelines on PrEP, the World Health Organization (WHO) stated that “PrEP can also be considered as an additional prevention choice for HIV-negative pregnant women who are at substantial risk of HIV infection, as part of a comprehensive prevention of mother to child transmission (PMTCT) package” [12]. Currently, however, there is limited data on PrEP acceptability, initiation, and adherence in pregnant and breastfeeding women in high HIV incidence communities [2, 13-15].

PrEP for HIV involves the use of daily antiretroviral (ARV) medications to prevent HIV acquisition, similar to prophylaxis for malaria. Tenofovir (TDF) and tenofovir/emtricitabine (TDF/FTC) in a single tablet fixed-dose combination (FDC) are the ARV agents primarily used in oral PrEP studies to date, though studies of other formulations are under way. In December 2015, the TDF/FTC combination pill was approved for use as PrEP by the Medicine Control Council in South Africa, in combination with safer sexual practices [27]. Daily PrEP

may be used intermittently during periods of perceived HIV acquisition risk, rather than continually and lifelong, as is the case with ARV treatment. HIV testing, and estimation of creatinine clearance are recommended as baseline health measures. PrEP should not be given to those with abnormal renal function, nor should it be commenced in individuals with acute viral symptoms.

Source: AVAC Report 2013: Research & Reality: [http://www.avac.org/sites/default/files/infographics/PrEP\\_by\\_Numbers\\_jan2016.jpeg](http://www.avac.org/sites/default/files/infographics/PrEP_by_Numbers_jan2016.jpeg)

FIGURE 1: Effectiveness and adherence in trials of oral and topical tenofovir-based prevention.

To date there have been 10 randomized controlled trials of TDF-based PrEP reporting HIV outcomes. The studies have involved over 17,000 people and have demonstrated an overall reduction in HIV acquisition risk of 51% (women RR 0.57 [95% CI 0.34–0.94] and men RR 0.38 [95% CI 0.2–0.6]) [27-32]. Three studies in which there was high adherence to TDF (> 70% of drug detection) showed PrEP was most efficacious [27-30]. PrEP access is increasing in South Africa primarily in men who have sex with men (MSM) and sex workers. However, as of February 2018, only approximately 5000 people were on PrEP in South Africa, and there are two clinical trials ongoing in pregnant women in South Africa, including IMPAACT 2009, “Pharmacokinetics, Feasibility, Acceptability, and Safety of Oral Pre-Exposure Prophylaxis for Primary HIV Prevention during Pregnancy and Postpartum in Adolescents and Young Women and their Infants” which is an ongoing trial in Zimbabwe, Uganda, South Africa and Malawi (<http://impaactnetwork.org/studies/IMPAACT2009.asp>).

**PrEP safety in pregnant and breastfeeding women:** Studies of PrEP use in pregnancy and breastfeeding are more limited than those in nonpregnant adult populations. However, an increasing number of studies are addressing this question, and available evidence underscores its safety in this pregnancy and breastfeeding women and their infants (1–6). Importantly, a recent systematic review demonstrated that PrEP was not associated with increased pregnancy-related adverse events. No studies have found adverse effects among infants exposed to tenofovir disoproxil fumarate (TDF) as part of treatment for HIV-infected women during pregnancy [6–8] or breastfeeding [9–12]. Specifically, Mofenson et al’s systematic review identified seven studies of TDF in HIV-uninfected women. They report, “No statistically significant differences were observed between TDF and comparison non-TDF regimens in pregnancy incidence, stillbirth/pregnancy loss, preterm delivery less than 37 weeks, low birth weight <2500/<1500g, small for gestational age, birth defects, or infant (>14 days) or maternal mortality.” Their study concluded that “given available safety data, there does not appear to be a safety-related rationale for prohibiting PrEP use during pregnancy/lactation or for discontinuing PrEP use in HIV-uninfected women receiving PrEP who become pregnant and are at continuing risk of HIV

acquisition.” Based on the existing WHO guidelines and research, potential risks of PrEP adverse events outweigh the benefits of using PrEP when sexually active during pregnancy and breastfeeding periods.

**PrEP safety in young women:** There is very limited data on PrEP use specifically in pregnant adolescents less than 18 years of age (7–9). Very recently, one Phase II clinical trial has been completed in youth ages 15–17, looking at safety and feasibility in young men who have sex with men (10). This study demonstrated safety of TDF-FTC in 78 participants with only one adverse event possibly related to the study drug. There were no adverse effects on kidney function, liver function or bone density. A second study that includes adolescent girls has completed, but final results are not yet available (11). Finally, additional safety data is available from studies focused on the use of the TDF and FTC as antiretroviral therapy in HIV+ youth (7,12). One study looking at long term TDF use in 12- to 17-year-olds over a median of 96 weeks (longer than the proposed timeline of this study) showed no discontinuations due to the study drug and there was no significant decrease in bone mineral density, and kidney function was consistent with normal changes seen in adolescents. Thus, available data suggest that PrEP and its component drugs are safe in adolescent populations, though more studies are needed in both adolescents as a whole, and pregnant adolescents in particular.

**PrEP safety in infants:** Available data on infant outcomes after exposure to TDF-FTC suggest that there are no significant differences in health outcomes, including birth weight, preterm delivery, birth defects, or infant mortality, as summarized in a pair of recent systematic reviews (6,13). Long-term effects on infants have not been investigated in the context of PrEP, though this is becoming an area of active research, with studies such as IMPAACT 2009 focusing on both maternal and infant health outcomes after use of PrEP in the pregnancy and breastfeeding periods (14). However, one short-term study looked at drug levels in mothers and their breastfeeding infants in the context of PrEP treatment (5). They found that FTC was below 0.5% of the target therapeutic level given to infants to prevent postnatal HIV infection. TDF levels were even lower, <0.01% of target therapeutic levels and undetectable in 94% of infants.

Additional data on safety of TDF-FTC on HIV-uninfected infants is drawn from studies of HIV-infected mothers taking ART during pregnancy and breastfeeding while tracking health of infants who remain HIV-uninfected. One such study showed a mild decrease in infant serum phosphate levels between 6 and 12 months, but no decrease in serum creatinine levels with prolonged exposure (15).

No studies assessing long-term outcomes of infants exposed to PrEP are available. What data are available come from studies of health outcomes of HIV-uninfected infants in the context of ART use by HIV-infected mothers. One such study examined infant health after *in utero* TDF exposure with a median infant age of 25 months. This study found no differences in infant mortality, serum creatinine or phosphate levels, or immune cell function based on TDF exposure (16). In contrast, multiple studies demonstrate significant morbidity and mortality among infants exposed to HIV versus those who are not. One recent study looking at HIV-exposed, uninfected infants whose mothers were not on ART prior to labor and delivery, and who were subsequently formula-fed, found that up to 23% of infants had serious adverse events up to 6 months after delivery (17). Other studies have confirmed an increase in morbidity and mortality among HIV-exposed infants as compared to those not exposed, and are summarized in a recent meta-analysis that estimates HIV-exposure leads to a 70% increase in all-cause mortality, corresponding to a risk-ratio of 1.70 (18). However, this increased risk is attributed to HIV exposure, not TDF exposure (18).

Though the data on short- and long-term infant outcomes after exposure to PrEP are limited, comparing available data of TDF exposure versus exposure to HIV during pregnancy and breastfeeding clearly indicate that preventing maternal HIV infection confers significant benefit to the infant as well as the mother. The

benefit of PrEP treatment of pregnant and breastfeeding women must thus consider both the dramatically decreased risk of infant HIV infection (0.5% for chronic vs. 30% for acute maternal HIV infections [19]) as well as the increase in all-cause mortality among HIV-exposed infants (a 70% increase versus those who are not HIV exposed). These two metrics clearly demonstrate that the benefits of PrEP outweigh the minor risks by at least 5:1.

**Side effects of PrEP:** Side effects associated with FTC/TDF include diarrhea, nausea, fatigue, headache and rash, which are seen in about 10% of participants during the initiation of therapy [33]. While these early symptoms are generally well-tolerated and dissipate over a few weeks, such side effects may be less tolerable for pregnant or postpartum women. For HIV-infected pregnant and postpartum women, such risks – including the adverse bone and renal effects of TDF – are offset by the significant health benefits of taking the drug as part of ART. However, the risk of adverse drug effects in relation to the potential HIV prevention benefits for HIV-uninfected women at increased risk for infections requires further evaluation. Tenofovir is a highly-charged anion that does not readily permeate across epithelial barriers. The water soluble pro-drug administered by mouth, TDF, is well absorbed in the gut and is rapidly converted to the active form, tenofovir. While tenofovir is present in amniotic fluid and cord blood, a study of 50 HIV uninfected lactating women receiving 10 days of directly observed oral dosing with TDF/FTC PrEP found low infant drug levels and breastmilk penetration [11]. This suggests the risk of postnatal exposure to PrEP in breastfed infants is low.

**Renal damage:** TDF use has been associated with a small and asymptomatic decrease in glomerular filtration rate in HIV-infected individuals. Reports from completed PrEP clinical trials reveal no clinically significant elevations in serum creatinine but transient decrease in estimated glomerular filtration rates and a return to baseline levels within four weeks of PrEP discontinuation [34]. PrEP is not recommended for people with decreased renal function at baseline (GFR < 60ml/min).

**Bone demineralization:** Consistent with data on reduced bone mineral density (BMD) among HIV-infected adults on ARVs, PrEP use has been associated with an approximate 1% reduction in BMD among trial participants [35]. The effect on BMD was shown to be reversible in young African women adherent to PrEP in the VOICE trial with a follow-up dual-energy x-ray absorptiometry (DXA) scan 48 weeks after stopping study drug [35].

[figure not shown]
**Adverse pregnancy outcome:** A secondary analysis from the Partners PrEP study found no differences between women with incident pregnancies while taking PrEP in rates of preterm birth, congenital anomalies, or infant growth in the first year of life and women taking placebo; however, all women stopped the study medication at time of pregnancy detection, which occurred a median of 35 days (IQR: 29–45) after conception [36]. The rates of adverse birth outcomes did not differ according to study arm (78). The Partners Demonstration Project, an open-label delivery study in Kenya and Uganda, HIV-uninfected women in serodiscordant relationships were given the option of continuing PrEP even after pregnancy was diagnosed. Of the 34 who became pregnant, 30 elected to continue PrEP antenatally. When compared to 96 women who became pregnant in the Partners PrEP clinical trial, there were no differences in pregnancy loss, preterm delivery, or congenital anomalies, though sample sizes were small [36].

**HIV and pregnancy in young women:** Young South African women aged 15–24 years contribute nearly 30% of all new HIV infections in the region. In South Africa, this percentage translates to 113,000 new infections in young women per year, more than four-times the number contributed by their male peers (Figure 2). Further, adolescent girls have high pregnancy rates in South Africa. Approximately 3.7% of 16-year-old girls and 7% of 17-year-old girls were pregnant in 2013 (Figure 3).

[figure not shown]
Our study proposes to enroll pregnant adolescents 16-17 who provide their assent to participate in the study. The specific age range – enrollment of adolescent and young women 16-19 years – covers a critical period of risk of HIV acquisition. This age range falls squarely within the period of adolescence defined by the World Health Organization as 10-19 years of age. Because of the high HIV incidence and existing policy supporting ~~PrEP~~ ~~adolescent girls in South Africa to not have sex with young women with PrEP~~ young women with PrEP

**Figure 2.** HIV incidence (%) by age and sex in South Africa

Our team is comprised of highly experienced adolescent HIV prevention researchers, including [name] and [name], who have a long history of research that seeks to address the key health issues facing South African adolescent girls while at the same time protecting this vulnerable population. The research sites have considerable experience in conducting clinical research in adolescent populations.

**Figure 3.** Adolescent pregnancy in South Africa, 2010-2013

Our study, PrEP-PP (PrEP in Pregnant and Postpartum women) will determine the distribution of women across the PrEP cascade (i.e. PrEP initiation, retention, and adherence) in a cohort of HIV- pregnant and breastfeeding

adolescent girls and women in two public health facilities in South Africa to inform policymakers about the efficacy of PrEP integration into antenatal (ANC) and postnatal care in high HIV incidence communities.

## **2. Study objectives:**

The objectives of the study are to:

### **1. Determine the distribution of women across the PrEP cascade:**

- (1) Evaluate the proportion of pregnant and breastfeeding women who initiate PrEP out of all women offered PrEP**
- (2) Evaluate the proportion of pregnant and breastfeeding women who are retained in the PrEP cohort**
- (3) Evaluate the proportion of pregnant and breastfeeding women who initiate PrEP who adhere to PrEP using objective dried blood spot measures and subjective measures of self-reported pill count and adherence**
- (4) Evaluate the proportion of pregnant and breastfeeding women on PrEP (and not on PrEP) who acquire HIV, who transmit HIV to their infant, and who report adverse events**

- 2. Evaluate patient and provider-level factors associated with the PrEP cascade using quantitative and qualitative approaches (including in-depth interviews)**
- 3. Apply an established mathematical model to simulate the impact of improvement in the PrEP cascade on HIV infections averted (maternal and perinatal)**
- 4. Evaluate the effect of PrEP on vaginal microbiome in pregnant women and the consequent relationship to adverse pregnancy outcomes.**

## **3. Study design**

To address these objectives, we will conduct an observational cohort study in 1200 pregnant women who will be recruited at the first antenatal care (ANC) visit from the Gugulethu and one additional facility in the Hanover Park subdistrict of the Metro Region (to be identified in conjunction with provincial and local health authorities) Midwife Obstetric Units in Cape Town (n=600 pregnant women per site). We will follow the enrolled women through 12-months post-delivery.

**Setting.** The study will take place in two urban townships in Cape Town (Gugulethu and Hanover Park) with high HIV incidence that span the different socioeconomic, cultural, and ethnic groups in South Africa.

- Site 1: Gugulethu Midwife Obstetrics Unit (MOU)**
- Site 2: Hanover Park**

We selected those communities because of the high HIV prevalence there in pregnant and breastfeeding women, and because of the high number of mothers visiting every month for ANC and labour/delivery. Further, our team has several years' experience implementing research studies in those MOUs which will facilitate the integration of the study there. In 2017, Gugulethu saw over 3300 new ANC consultations per month, and 72%

(n=2300) are HIV-negative. Hanover Park has saw over 4900 new ANC consultations/month of which 87% are HIV-negative (n=4200). Considering our experience and patient flow, we are confident that at least 60 women/month per facility can be enrolled. Further, Drs. [name], [name] and colleagues have conducted research in the Gugulethu and Hanover Park communities for more than a decade and have substantial experience partnering with local health services. Building on this platform, we will use existing infrastructure in each clinic, including capacitating existing clinical providers, pharmacists and counselors, to provide PrEP care to pregnant and breastfeeding mothers. We will hire study staff to assist in the coordination, data management, and overall quality assurance of the counseling, drug provision and participation follow-up.

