##### Inclusion Criteria:

- 1.  $\geq 16$  years old**
- 2. confirmed HIV-negative (confirmed with a 4th generation antigen HIV test)**,
- 3. Intend on giving birth in the MOU facility**
- 4. confirmed to be pregnant**
- 5. without psychiatric or medical contraindications to PrEP.**

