## **6. Analytic Considerations**

### Sample size considerations

The projected sample size for the study is 1200 women enrolled from 1st ANC visit until 12-months postpartum (estimated mean of 18-months follow-up). This estimate is based on the following assumptions:

- (1) 60% of women will initiate PrEP during the study period (versus approximately 40% who will not);**
- (2) Approximately 75% of women on PrEP will be retained in care at 12-months (defined as not missing >1 study visit among women on PrEP)**
- (3) 70% of those retained in care (n=378) will adhere to PrEP during at-risk periods.**

A sample size of 1200 women yields 80% power to detect identify a relative risk of 2.0 or greater in key covariates including age (<25 vs.  $\geq$ 25 years), pregnancy and relationship status associated with PrEP initiation versus non-initiation. A sample size of 378 women (e.g. 70% of women retained in the study on PrEP will be adherent as measured by TDF-DP measures) yields 80% power to detect relative risks of 2.0 or greater associated with adherence in the cohort. The analysis will be based on women who complete the 12-month postpartum cohort follow up. We will use relative risk ratios performed at a two-sided  $\alpha$  level of 0.05.

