## Sample size considerations

The projected sample size for the study is *1200 women enrolled from 1st ANC visit until 12-months postpartum (estimated mean of 18-months follow-up)*. This estimate is based on the following assumptions:

- (1) 60% of women will initiate PrEP during the study period (versus approximately 40% who will not);
- (2) Approximately 75% of women on PrEP will be retained in care at 12-months (defined as not missing >1 study visit among women on PrEP)
- (3) 70% of those retained in care (n=378) will adhere to PrEP during at-risk periods.

A sample size of 1200 women yields 80% power to detect identify a relative risk of 2.0 or greater in key covariates including age (<25 vs. >25 years), pregnancy and relationship status associated with PrEP initiation versus non-initiation. A sample size of 378 women (e.g. 70% of women retained in the study on PrEP will be adherent as measured by TDF-DP measures) yields 80% power to detect relative risks of 2.0 or greater associated with persistence in the cohort. The analysis will be based on women who complete the 12-month postpartum cohort follow up. We will use relative risk ratios performed at a two-sided  $\alpha$  level of 0.05.

## Statistical analysis considerations for AIMS 1 & 2

The primary analysis for *Aim 1* will focus on measuring the distribution of women across the PrEP cascade including: initiation, continuation and persistence. **PrEP initiation** will be based on a woman's uptake of PrEP and allow for stoppage and re-initiation; **PrEP continuation** will be defined as not missing >1 visit among those on PrEP (with separate analyses of PrEP stoppage). For **PrEP persistence** for women on PrEP we will measure both *perfect persistence* (i.e. level of objective persistence throughout pregnancy and breastfeeding periods) as well as "*prevention-effective*" persistence (i.e. persistence during times of sexual activity) in participants through objective and subjective measures to evaluate agreement between the two measures, and the level of under- or over-reporting. Primary persistence analyses will use objective measures (TDF-DP from DBS) taken on all those who enrolled and initiated PrEP; subsidiary analyses will consider (i) other persistence measures and (ii) multiple imputation for missing persistence data.

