#### ***Methods/Approach:***

- (1) Study flow figure (see Continuation Flowcharts)
- (2) Number screened per week and month (target= 18 per week, 72 per month) vs number enrolled
  - a. The projected sample size for the study is 1200 women enrolled until 12-months postpartum (estimated mean of 18-months follow-up).
- (3) Subjects initiating PrEP compared to those who do not
  - a. Estimated that 60% of women (n=720) will initiate PrEP during the study period (versus approximately 40% who will not).
- (4) Continuation and persistence by group
  - a. Assumed that approximately 75% of women on PrEP (n=540) will continue on PrEP at 12-months (defined as not missing >1 study visit among women on PrEP);
  - b. Assumed that 70% of those retained in care (n=378) will adhere to PrEP during at-risk periods.
- (5) Final completion rates
  - a. Compare final number of participants who enroll in study, who initiate PrEP, who are retained in care, and who adhere to PrEP to sample sizes needed to yield 80% power (i.e., n=1200, 720, 540, 378, respectively).
- (6) Number of subjects in analysis data sets
  - a. Consider number of participants that will potentially be excluded from analyses because of withdrawal from study, missing data on key covariates or outcomes, etc.

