#### **Methods/Approach:**

Construct “Table 1” describing the baseline characteristics of each intervention group including:

- (1) Demographic characteristics (e.g., age, socioeconomic status, ethnicity, gestational age at baseline, number of children, knowledge of PrEP, relationship status, risk factors)
- (2) Baseline exposure characteristics (e.g., PrEP initiation)
- (3) Baseline disease characteristics (i.e., STI results)
- (4) Baseline values of primary and/or secondary outcome variables (note, this may be a separate table)

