***Methods/Approach:***

Tabulation of adverse effects with each treatment group:

- (1) Number of events by type of event
  - Describe the frequency of any laboratory or self-reported side effects (e.g. changes in creatinine clearance, or self-reported side-effects [GI symptoms, headache, and etc]). Analyses will include pure-count and person-time approaches. Confidence intervals will be calculated following the method of Breslow and Day. We will also describe pregnancy (miscarriage, stillbirth) and infant outcomes over time (including birthweight, gestational age at delivery, pregnancy loss) by PrEP status (on/off PrEP and by persistence to PrEP)
- (2) Number of subjects by highest grade of event
- (3) Reasons for termination of treatment

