#### Part 4: Birth outcomes (by PrEP status for analysis)

	Frequency	Percentage	Comment
Number of active participants			
Number of women still pregnant			
Number of Births, (n=X)			
Number of Live Births			
Number of Birth abnormalities			
Still births			
Miscarriage			
Other			

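### Miscarriage and total pregnancy loss are compared by PrEP use as plain percentages, with no allowance for the different gestations at which women enter the cohort

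*Combined protocol and SAP*

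**What the plan says.** **Entry.** Protocol section 3 plans for "1200 pregnant women who will be recruited at the first antenatal care (ANC) visit". On pregnancy, the inclusion criteria ask only that the woman is "confirmed to be pregnant". No inclusion or exclusion criterion sets a lowest or highest gestational age.

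**Comparison.** SAP 2.6 states: "We will also describe pregnancy (miscarriage, stillbirth) and infant outcomes over time (including birthweight, gestational age at delivery, pregnancy loss) by PrEP status". SAP Table 1 lists negative maternal and neonatal outcomes as a secondary outcome, to be compared between PrEP use and non-use. The birth-outcome shell in SAP section 4 has a number and a percentage column for users and for non-users, with rows for live births, abnormalities, stillbirths, miscarriage and other. Part 4 of the report templates repeats these rows, marked for analysis by PrEP status. Both shells also have a row for "Number of women still pregnant", but neither says what the percentages are a percentage of.

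**Gestation at entry.** SAP 2.3 puts "gestational age at baseline" in the baseline table, and the demographic template has gestational-age rows. Nothing in SAP 2.6 or the shells carries it into the pregnancy-outcome comparison.

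**The concern.** A pregnancy can be lost under observation only after the woman has enrolled. Weekly loss risk falls steeply with gestation, so a woman who enrols late has already survived the worst weeks. A woman who enrols after the miscarriage limit cannot have that event at all. This is left truncation, and a plain percentage ignores it.

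Two consequences follow:

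- If users and non-users enter at different gestations, the group that enters earlier shows more miscarriage even when PrEP does nothing. Depending on direction, the comparison can suggest harm, suggest protection, or hide a real effect.
- If women who enter after the limit stay in the denominator, the miscarriage percentage understates the risk among women who could miscarry. This needs no group difference.

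The study is meant to inform policy on PrEP in antenatal care, and the report templates are intended partly for the DSMB. A loss percentage by PrEP use will be read as safety evidence.

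**Working it through.** **Figures from the plan**

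- SAP 2.2: "Estimated that 60% of women (n=720) will initiate PrEP during the study period". 1200 × 0.60 = 720, as stated, which leaves 1200 − 720 = 480 non-initiators.
- Sample size section: "estimated mean of 18-months follow-up", including 12 months postpartum. 18 − 12 = 6 months, about 26 weeks, before delivery. With delivery at 40 weeks, mean entry is 40 − 26 = 14 weeks. Allowing for early censoring would make it earlier.
- Weekly loss risk, spread of entry gestation, the miscarriage limit and any entry difference between groups: not given. All are assumed below.

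**Hand check with no PrEP effect**

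Assumed weekly loss risk: 1.0% before week 12, 0.4% in weeks 12–15, 0.2% in weeks 16–19, 0.08% after. Miscarriage is counted before 28 weeks. Risk after entry = 1 − product of (1 − weekly risk) from the entry week to week 27.

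- Entry at 14: 1 − 0.996² × 0.998⁴ × 0.9992⁸ = 2.22%
- Entry at 16: 1 − 0.998⁴ × 0.9992⁸ = 1.43%
- Entry at 18: 1 − 0.998² × 0.9992⁸ = 1.04%

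The ratios are 2.22/1.43 = 1.55 for 2 weeks and 2.22/1.04 = 2.1 for 4 weeks.

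**Entry spread around the mean**

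Same risks in both groups (true ratio 1.0), entry SD 6 weeks, range 6–36, 480 non-users and 720 users, with users entering later:

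| Mean entry, non-users vs users | Miscarriage | Ratio of percentages | Ratio per person-week from entry | Ratio by gestational week, delayed entry |
|---|---|---|---|---|
| 14 vs 16 | 2.7% vs 2.1% | 0.79 | 0.84 | 1.00 |
| 14 vs 18 | 2.7% vs 1.6% | 0.60 | 0.68 | 1.00 |
| 14 vs 20 | 2.7% vs 1.2% | 0.44 | 0.54 | 1.00 |

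The first two inverses are 1/0.79 = 1.27 and 1/0.60 = 1.67. Halving or doubling the risks hardly moves the ratios. Over that range, the chance of a nominally significant result at two-sided 0.05 is 0.07–0.15, 0.16–0.45 and 0.30–0.77 for the three rows.

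**A second set of assumptions**

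Weekly risk 2% before week 8, 1% in weeks 8–11, 0.4% in 12–15, 0.2% in 16–19, 0.1% in 20–27, 0.06% from 28; SD 7; miscarriage limit 20 weeks.

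- Entry 18 vs 20 weeks: miscarriage ratio 1.45 (1.55 with SD 6); any loss 1.24.
- Entry 18 vs 22 weeks: miscarriage about 2.2 (about 2.7 with SD 6); any loss 1.56.
- Entry 14 vs 16 weeks: miscarriage 1.33, or 1.26 with a 28-week limit.

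Across these inputs the miscarriage ratio is roughly 1.3–1.6 for 2 weeks and 1.7–2.7 for 4 weeks.

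**Other outcomes**

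Under the first set, with non-users entering at 14 weeks, the stillbirth ratio is 0.99–1.01 and the preterm ratio 1.00–1.03. With late entry (22 vs 26 weeks) they are 0.94–0.95 and 0.98–0.99. Under the second set, 18 vs 20 weeks, stillbirth is 1.05 with a 20-week limit and 1.01 with a 28-week limit.

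**Restricting the miscarriage denominator only**

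For 18 vs 20 weeks under the second set, limiting the row to women enrolled before the limit lowers the ratio from about 1.47 to 1.18 with a 20-week limit, and from about 1.35 to only 1.27 with a 28-week limit.

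**The case against.** *The groups may not differ at entry.* This is the strongest point and it stands as a condition. Every woman is offered PrEP at the enrolment visit, and no section gives or predicts a difference in gestation between takers and decliners. A reader might infer that the comparison is bound to be biased. The documents support only that it can be, in either direction.

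*Baseline gestation is already tabulated.* It is, and the template allows a split by PrEP status. An imbalance could then be seen, but nothing in the plan corrects for it.

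*SAP 2.6 mentions person-time.* That sentence follows the one on laboratory and self-reported side effects, comes before pregnancy outcomes are mentioned, and names no time origin. Person-weeks counted from entry would still give 0.84, 0.68 and 0.54 where the truth is 1.0.

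*Covariates are chosen with causal diagrams.* That text belongs to the models for initiation, continuation and persistence. No model is given for birth outcomes.

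*The outcome is secondary and descriptive, and final paper tables are built separately.* This is true. No test or power is stated for it, and for a 2-week difference the chance of nominal significance is little above 0.05. This limits the weight of the point. The SAP still presents the outcome as a comparison.

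*Stillbirth and preterm birth.* A reader might extend the point to both. Preterm birth is a named adverse outcome in the protocol but has no row in the shells, and both are barely distorted unless entry is late.

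**Conclusion.** The point holds for miscarriage, and through it for total pregnancy loss. The plan has open-ended entry, a percentage comparison by PrEP use, and no use of entry gestation in it. With no PrEP effect, a 2-week entry difference alone can give a miscarriage ratio of about 1.3–1.6 (or its inverse), and a 4-week difference 1.7–2.7. For any loss, the second set of assumptions gives 1.24 and 1.56. These sizes rest on assumed weekly risks, entry spread and miscarriage limit. The ratios are insensitive to the overall level of risk but do depend on the entry difference, which is unknown.

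The understatement of the miscarriage percentage depends on the same unknowns, and on late entrants being counted in the denominator. A reader might conclude that half the cohort cannot miscarry. That requires both a mean entry of 20 weeks and a 20-week limit, and the documents state neither. At the 14-week mean implied by the follow-up figure, the share is about 20% with a 20-week limit and about 2% with a 28-week limit.

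The primary cascade analyses are not touched. This is a correction that should be made to a secondary safety comparison.

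**What to change.** In SAP 2.6, and for the birth-outcome tables by PrEP status in section 4:

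- Analyse miscarriage and any pregnancy loss on the gestational-age time scale, with each woman entering the risk set at her gestation on enrolment.
- Treat PrEP status as time-updated. The SAP allows PrEP to start at any time in the study, so a woman who starts later must have stayed pregnant until then; the same analysis deals with this.
- State the gestational limit that separates miscarriage from stillbirth, and the denominator of each percentage.
- Show gestation at entry by PrEP group beside the table.

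If percentages are kept, limit the miscarriage row to women enrolled before that limit **and** stratify by gestation at entry, since restriction alone removes only part of the bias.

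The cost is SAP wording and a little more analysis work. Gestation at entry is already collected; dates of PrEP use and of loss are also needed, and I assume that these are recorded. The miscarriage row will have a smaller denominator and a wider interval.
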